2.2 IND Agent

Clofarabine (2-chloro-9-[2'-deoxy-2'-fluoro-β-D-arabinofuranosyl] adenine; Cl-F-ara A; CAFdA) is a rationally designed, second generation purine nucleoside analogue. Clofarabine was designed as a hybrid molecule to overcome the limitations and incorporate the best qualities of both fludarabine (F-ara-A) and cladribine (2-CdA, CdA) both of which are currently approved by various regulatory authorities for treatment of hematologic malignancies. Because clofarabine has a chloro- group at the 2-position of adenine, its chemical structure is more closely related to 2-CdA than to F-ara-A. Halogenation at the 2-position of adenine renders this class of compounds resistant to intracellular degradation by the enzyme

CONFIDENTIAL

This document is confidential. Do not disclose or use except as authorized.

adenosine deaminase. Substitution of a fluorine at the C-2'-position of the arabinofuranosyl moiety of clofarabine increases its stability in gastric acid^{50,51} and decreases its susceptibility to phosphorolytic cleavage by the bacterial enzyme *Escherichia coli* purine nucleoside phosphorylase in the gastrointestinal tract,⁵¹ both of which may lead to enhanced oral bioavailability. Clofarabine was approved in December 2004 by the United States Food and Drug Administration (US FDA) for the treatment of pediatric patients with relapsed or refractory acute lymphoblastic leukemia (ALL) after at least 2 prior regimens based on the induction of complete responses.

2.2.1 Mechanism of Action

The precise mechanism of action of clofarabine on dividing and non-dividing cells is unknown. Like other nucleoside analogues (cytarabine, cladribine, and fludarabine), clofarabine must be converted within cells to the 5'-triphosphate form by deoxycytidine kinase (dCK) and mono- and di-phosphokinases to be active. Clofarabine is more efficient as a substrate for purified recombinant dCK, exceeding cladribine and the natural substrate, deoxycytidine.⁵² Evidence suggests that the primary cytotoxic effect of clofarabine is due to its inhibition of DNA synthesis and repair. The triphosphate form of clofarabine is an inhibitor of both DNA polymerase α and ϵ and ribonucleotide reductase.⁵³ These inhibitory effects lead to depletion of intracellular deoxynucleotide triphosphate pools and inhibition of elongation of DNA strands during synthesis and DNA repair.⁵⁴ With respect to inhibition of ribonucleotide reductase, clofarabine and cladribine are superior to fludarabine.⁵² With respect to inhibition of DNA polymerase α , clofarabine and fludarabine are similar and both are superior to cladribine.⁵² Thus, in comparison to cladribine and fludarabine, clofarabine more completely inhibits both ribonucleotide reductase and DNA polymerase α , versus one or the other.

Unlike fludarabine, clofarabine is active in vitro in non-dividing cells and in cells with a low proliferation rate. Clofarabine can induce the apoptotic pathway as part of its cytotoxic effect on cells.⁵¹ Clofarabine has been shown to disrupt the integrity of mitochondria in primary chronic lymphocytic leukemia (CLL) cells. The damage leads to release of pro-apoptotic mitochondrial factors.⁵⁵ These effects are postulated to induce apoptosis in indolent, non-dividing CLL cells. This result was not seen with fludarabine and may explain, at least in part, the enhanced cytotoxicity of clofarabine,⁵⁵ although the physiologic and clinical implications of these observations remain uncertain and under continued investigation.

2.2.2 Pharmacokinetics and Pharmacology

Pharmacokinetics of Clofarabine in Adult Patients with Acute Myeloid Leukemia (AML)

Pharmacokinetic data were collected from 13 adult patients with refractory or relapsed AML in an open-label study in which they were treated with clofarabine 40 mg/m²/day IV infusion over 1 hour for 5 consecutive days.⁵⁶ Stationary pharmacokinetics were observed between Days 1 and 5, and plasma concentrations declined rapidly thereafter and exhibited biphasic kinetics. The estimated terminal half-life was approximately 6 hours and ranged from 4.1 to 8.6 hours. Consistent with this short half-life, pre-dose concentrations on Day 2 were about 10% or less of maximal concentrations at the end of infusion. After 4 days of dosing, pre-dose concentrations

CONFIDENTIAL

This document is confidential. Do not disclose or use except as authorized.

averaged 13.8 ng/mL and ranged from 4.0 to 23.1 ng/mL. Because of the short half-life of clofarabine, there was little-to-negligible accumulation with once daily dosing of clofarabine at 40 mg/m² by 1-hour IV infusion.

Pharmacokinetics of Clofarabine in Pediatric Patients with Acute Lymphoblastic Leukemia (ALL)

The population pharmacokinetics of clofarabine was studied in 40 pediatric patients aged 2 to 19 years (21 males/19 females) with relapsed or refractory ALL or AML. At the given 52 mg/m² dose, similar concentrations were obtained over a wide range of body surface areas (BSAs). Clofarabine was 47% bound to plasma proteins, predominantly to albumin. Based on non-compartmental analysis, systemic clearance and volume of distribution at steady-state were estimated to be 28.8 L/h/m² and 172 L/m², respectively. The terminal half-life was estimated to be 5.2 hours. No apparent difference in pharmacokinetics was observed between patients with ALL and AML or between males and females. No relationship between clofarabine or clofarabine triphosphate exposure and toxicity or response was found in this population. Based on 24-hour urine collections in the pediatric studies, 49-60% of the dose is excreted in the urine unchanged. In vitro studies using isolated human hepatocytes indicate very limited metabolism (0.2%), therefore the pathways of non-renal elimination remain unknown.

Although no clinical drug-drug interaction studies have been conducted to date, on the basis of the in vitro studies, cytochrome p450 inhibitors and inducers are unlikely to affect the metabolism of clofarabine. The effect of clofarabine on the metabolism of cytochrome p450 substrates has not been studied. The pharmacokinetics of clofarabine have not been evaluated in patients with renal or hepatic dysfunction.⁵⁷

Peripheral blood mononuclear cell (PBMC) clofarabine triphosphate concentrations were assessed in selected pediatric patients with relapsed or refractory ALL or AML in the pivotal Phase 2 studies of clofarabine (Genzyme Corp. Data on file).⁵⁸ Triphosphate concentrations were similar in magnitude to adults given the same or similar dose. The half-life of the triphosphate could not be adequately characterized but was estimated to be greater than 24 hours. No correlation between triphosphate concentrations and either dose or parent clofarabine concentration was found.

2.3 Rationale for the use of clofarabine in recurrent or refractory LCH

Clofarabine is a second-generation deoxyadenosine analog, designed to improve the efficacy and minimize the toxicity of its congeners cladribine and fludarabine. Whereas fludarabine triphosphate primarily inhibits DNA polymerases and cladribine triphosphate particularly inhibits ribonucleotide reductase, clofarabine triphosphate inhibits both DNA polymerases and ribonucleotidase reductase in addition to inducing apoptosis through release of mitochondrial cytochrome C. The cellular retention of phosphorylated clofarabine metabolites is longer than that of other purine nucleoside analogues. Clofarabine has demonstrated significant activity in ALL, AML, and MDS including patients refractory to other deoxyadenosine analogs.⁵⁹⁻⁶³ In a Phase I trial of clofarabine in children with refractory hematologic malignancies, DLT at 70 mg/m²/day x 5 days was hyperbilirubinemia and skin rash, and MTD was 52 mg/m²/day for 5 consecutive days.⁶² In a subsequent Phase II study using the MTD in children with

CONFIDENTIAL

This document is confidential. Do not disclose or use except as authorized.

recurrent or refractory ALL response rate was 30%.⁶¹ At this dose, toxicity was characterized by electrolyte abnormalities (hypokalemia, hypophosphatemia) and mild elevation of liver enzymes and bilirubin. Two-thirds of the patients developed severe (\geq grade 3) infectious complications, including sepsis and septic shock (20% of patients).⁶¹

The optimal treatment for patients with RDD, JXG, ECD, HS, and IDCMH is not established. In particular, the prognosis of HS and IDCMH remains poor. Although there is a reasonable amount of data in the literature to support the use of interferon and BRAF inhibitors in ECD, the optimal treatment of ECD refractory to these agents and the optimal treatment of HS, JXG, and IDCMH remain to be defined. Therefore, given the paucity of data and the activity of clofarabine in LCH, inclusion of these histologies in the present trial is justified.

Study and Dose Rationale

The safety profile of clofarabine appears acceptable within the target populations studied to date in the clinical studies summarized above, and clofarabine has demonstrated anti-cancer activity through inhibition of DNA synthesis and repair, induction of apoptosis, and possibly through other mechanisms. Numerous responses have been observed after treatment with clofarabine in heavily pre-treated relapsed/refractory patients with ALL or AML. As documented above, there is also a strong rationale for

CONFIDENTIAL

This document is confidential. Do not disclose or use except as authorized.

the study of clofarabine in refractory LCH, although a less intensive regimen may be effective. In this study, a dose of 25 mg/m²/day will be administered for 5 days. Evaluation of response will be performed after 2 cycles, and participants showing response will receive four additional cycles of clofarabine at the same dose for the first 5 days in each cycle. The selected dose is significantly lower than the maximum tolerated dose of 52 mg/m²/d defined in pediatric phase I trials; this lower dose has been selected based on the excellent response rates noted in patients with recurrent or refractory LCH using doses of 25-30 mg/m²/d.^{64,65}

3 PARTICIPANT SELECTION

Patients will undergo baseline/screening procedures as defined in Table 2 within 14 days prior to starting protocol therapy.

Stratum 1: Recurrent or Refractory LCH

Participants with multi-focal or multi-system disease who have recurred after at least one prior systemic chemotherapy regimen.

Stratum 2: LCH-Related Disorders Requiring Systemic Therapy

Participants with LCH-related disorders who require systemic chemotherapy including: Participants with RDD who have not responded to or recurred after treatment with corticosteroids. ECD subjects who have confirmed presence of BRAF V600E mutation must have not responded to, have recurred after, or be unable to receive treatment with a BRAF inhibitor.

Laboratory tests required for eligibility must be completed within 14 days prior to study entry. Baseline tumor measurements and other studies must be performed within 30 days of study entry.

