The treatment of LCH over the years has reflected the changing concepts of the disease process. Indeed, the difficulties in developing more effective therapies are linked to the deficiencies in the understanding of the pathogenesis of LCH. Retrospective studies of Lahey⁶ and Komp et al⁷ showed that, although many organs can harbor proliferating Langerhans cells, only if organ function were disrupted was such involvement of prognostic significance. Patients could then be stratified into different risk categories based on the extent of their disease and the degree of organ dysfunction. Two large cooperative trials^{8,9} later confirmed those findings, and also identified a subgroup of patients (defined by age > 2 years and absence of organ dysfunction) with an excellent prognosis despite multi-system involvement. Treatment for patients with LCH is currently risk-adapted. Patients with single-system disease confined to a single site usually require only local therapy or observation. Patients with more extensive disease (multiple bone lesions or multiple lymph nodes) usually require systemic therapy. The best therapeutic option in these cases has not been defined, and responses have been observed with short courses of steroids with or without the addition of chemotherapeutic agents.¹⁰ The treatment recommended by the Histiocyte Society for this group of patients includes a 6-week induction with prednisone and vinblastine, followed by continuation treatment with pulses of the same agents every 3 weeks. The prognosis for this group of patients is usually excellent, although approximately 30% of the patients will experience disease reactivations that continue to respond to treatment.

CONFIDENTIAL

This document is confidential. Do not disclose or use except as authorized.

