3.1 Inclusion Criteria

Participants must meet the following criteria on screening examination to be eligible to participate in the study:

1. Prior diagnosis of Langerhans Cell Histiocytosis (stratum 1) or LCH-related disorder (stratum 2) established by standard diagnostic criteria and confirmed histologically.
2. Evidence of active disease (histological confirmation of reactivation or progression is not required).
3. Performance Score > 70% (use Lansky score for age <16 and Karnofsky score for age ≥16, see Appendix I).
4. Patients of all ages will be eligible.
5. Provide signed written informed consent.

CONFIDENTIAL

This document is confidential. Do not disclose or use except as authorized.

6. In stratum 1, patients must have failed one prior systemic chemotherapy regimen. In stratum 2, RDD patients must have failed treatment with corticosteroid. EDC patients who have confirmed BRAF V600E mutations must have failed treatment with BRAF inhibitor or are not considered to be eligible for such treatment.
7. There is no limitation of amount or the type of prior therapy or drugs.
8. Female patients of childbearing potential must have a negative serum pregnancy test within 14 days prior to enrollment. Male and female patients must use an effective contraceptive method during the study and for a minimum of 6 months after study treatment.
9. Capable of understanding the investigational nature, potential risks and benefits of the study, and able to provide valid informed consent.
10. Participants must have adequate marrow functions as defined below, except those who involvement of hematopoietic system for whom these criteria can be waived:
 - Absolute neutrophil count ≥ 750 cells/ μ L
 - Platelets ≥ 750 cells/ μ L
11. Participants must have adequate organ function as defined below:
 - Total bilirubin ≤ 2.5 x institutional upper limit of normal.
 - AST (SGOT)/ALT (SGPT) < 2.5 x institutional upper limit of normal unless it is related to involvement by LCH.
 - Pediatric Population (patients < 18 years): Creatinine within normal limits or calculated creatine clearance ≥ 90 mL/min/1.73 m² as calculated by the Schwartz formula for estimated glomerular filtration rate (GFR) where GFR (mL/min/1.73 m²) = k x Height (cm)/serum creatinine (mg/dL). k is proportionally constant which varies with age and is a function of urinary creatine excretion per unit of body size; 0.45 up to 12 months of age; 0.55 children and adolescent girls; and 0.70 adolescent boys.

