3.2 Exclusion Criteria

Participants who exhibit any of the following conditions at screening will not be eligible for admission into the study.

1. Participants who have had chemotherapy or radiotherapy within 2 weeks (6 weeks for nitrosoureas or mitomycin C) prior to entering the study or those who have not recovered from adverse events due to agents administered more than 2 weeks earlier. Corticosteroid treatment is allowed.
2. Participants may not be receiving any other investigational agents targeting Histiocytosis.
3. Clofarabine is excreted primarily by the kidneys. Therefore, drugs with known renal toxicity (e.g. vancomycin, amphotericin B, acyclovir, cyclosporin, methotrexate, tacrolimus) should be avoided to the extent possible during the 5 days of clofarabine treatment in each cycle or, if required, administered cautiously and with close monitoring.
4. Use of alternative medications (e.g., herbal or botanical that could interfere with clofarabine) is not permitted during the entire study period.
5. Uncontrolled intercurrent illness including, but not limited to ongoing or active infection, symptomatic congestive heart failure, unstable angina pectoris, cardiac arrhythmia, or psychiatric illness/social situations that would limit compliance with study requirements.
6. Pregnant women are excluded from this study because clofarabine is a nucleoside analog with the potential for teratogenic or abortifacient effects. Because there is an unknown but potential risk of adverse events in nursing infants secondary to treatment of the mother with clofarabine, breastfeeding should be discontinued if the mother is treated with clofarabine. These potential risks may also apply to other agents used in this study.
7. Individuals with a history of a different malignancy are ineligible except for the following circumstances. Individuals with a history of other malignancies are eligible if they have been disease-free for at least 5 years and are deemed by the investigator to be at low risk for recurrence of that malignancy. Individuals with the following cancers are eligible if diagnosed and treated within the past 5 years: cervical cancer in situ, and basal cell or squamous cell carcinoma of the skin.
8. Patients with a history of prior hematopoietic stem cell transplantation (HSCT), elevated conjugated serum bilirubin at study entry, uncontrolled systemic fungal, bacterial, or other infection, a history of hepatitis B or C infection or a history of cirrhosis.

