8 STUDY CALENDAR

Baseline laboratory tests are to be conducted within 14 days prior to start of protocol therapy. Other evaluations (scans, pathology, EKG, etc.) must be done within 30 days of study entry. In the event that the participant's condition is deteriorating, laboratory evaluations should be repeated within 48 hours prior to initiation of the next cycle of therapy.

All assessments must be performed prior to administration of any study medication. All study assessments and medications should be administered within ± 3 days of the protocol-specified date, unless otherwise noted.

All follow-up assessments must be performed 12, 24, and 36 months from the off-treatment date (i.e. Day 28 of last administered cycle) ± 31 days.

A calendar for the time points when the required study data should be obtained is provided below.

CONFIDENTIAL

This document is confidential. Do not disclose or use except as authorized.

Table 2: Required Data / Study Calendar

Assessments	Baseline/ Screening (within 14 days)	Before Starting Each Cycle (within 3 days)	During Each Cycle	End of Cycle 2 ⁵	End of Treatment (+/- 7 days from day 28 of Cycle 6)	Follow- up ⁷ (+/- 31 days)
Informed Consent	X ¹					
Medical History Concurrent Condition Concomitant Medications/ Transfusions	X					
Height		X			X	
Weight		X			X	
BSA		X			X	
Physical exam/Vital Signs	X	X			X	
Performance Status	X ¹	X			X	
Hematology (CBC/Diff/Plts)	X ¹	X	Weekly ⁴		X	X ²
Electrolytes including Ca ⁺⁺ , PO ₄ , Mg ⁺⁺	X	X	Weekly ⁴		X	X ²
Creatinine, BUN, Serum glucose	X ¹	X	Weekly ⁴		X	X ²
LFTs (Total Protein/Alb., ALT, AST, ALP, Billi.)	X ¹	X	Weekly ⁴		X	X ²
Uric acid	X	X ²			X ²	
Serum β-HCG ³	X ¹				X	
EKG	X				X ²	
Urinalysis	X	X			X	
Bone Marrow Biopsy, Aspirate and Smear	X ² (within 30 days)			X ²	X ²	X ²
Disease Assessment/ Response Documentation (CT/MRI/ Bone Scan/ PET, as clinically indicated)	X ¹ (within 30 days)			X	X ⁶	X ⁸
Chest X-Ray PA and L	X				X	
Skeletal survey (stratum 1 only)	X			X	X ⁶	X ⁸
Clofarabine Administration			Days 1-5			
Adverse Event Assessment	X	X	Weekly ⁴		X	

¹ Source documents are required for eligibility review before registration.

² As clinically indicated.

³ For females of childbearing potential.

⁴ Weekly assessments are recommended as clinically indicated, to be completed every 7 days, +/- 3 days.

⁵ End of Cycle 2 assessments must be completed on Day 28 of Cycle 2 +/- 7 days, and prior to starting Cycle 3.

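### The baseline disease assessment is not required to follow the last prior treatment, so regression from earlier chemotherapy, radiotherapy or steroid can be counted as a clofarabine response

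*Combined protocol and SAP*

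**What the plan says.** **Baseline window.** Section 3 states "Baseline tumor measurements and other studies must be performed within 30 days of study entry". The section 8 text agrees: "Other evaluations (scans, pathology, EKG, etc.) must be done within 30 days of study entry". Table 2 gives the disease assessment row its own 30-day note. The opening of section 3 also sets a general window: "Patients will undergo baseline/screening procedures as defined in Table 2 within 14 days prior to starting protocol therapy". In Table 2 the stratum 1 skeletal survey sits in the 14-day column without the 30-day note.

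**Prior treatment.** Section 3.2 item 1 excludes "Participants who have had chemotherapy or radiotherapy within 2 weeks (6 weeks for nitrosoureas or mitomycin C) prior to entering the study", and the same item adds "Corticosteroid treatment is allowed", with no washout and no stable-dose condition. Section 3.1 item 7 says "There is no limitation of amount or the type of prior therapy or drugs".

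**Active disease.** Section 3.1 item 2 requires "Evidence of active disease (histological confirmation of reactivation or progression is not required"), without tying that evidence to a date after the last treatment. Item 6 requires stratum 1 patients to have failed one systemic regimen, which need not be the most recent treatment.

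**Endpoint.** In section 9, Tables 3 and 4 class any regression without new lesions as Better, with no minimum amount. Section 13.3 counts as a responder anyone whose best response is Better up to the End of Cycle 2 assessment. Section 13.1 describes a single-arm design.

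**The concern.** The primary endpoint is change from baseline with no comparator, so the baseline has to mark the disease state just before clofarabine. The plan fixes the latest date of prior chemotherapy or radiotherapy and the earliest date of the scan separately, and the two windows overlap. A patient may be scanned, complete a last course of chemotherapy or have a lesion irradiated, wait 2 weeks, enter, and be judged against the scan taken before that treatment.

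Steroids have the same gap and no washout at all. Section 2.1 reports, for LCH with multiple bone or nodal lesions, that "responses have been observed with short courses of steroids with or without the addition of chemotherapeutic agents".

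Because there is no size threshold for Better, a modest residual effect of earlier treatment is enough to be scored. Rule A needs 14 responders among 20, so one or two such patients could decide the result.

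**Working it through.** **1. Dates (day 0 = study entry).**
- Earliest baseline scan: day -30 (sections 3 and 8, Table 2).
- Latest permitted chemotherapy or radiotherapy: day -14 (section 3.2 item 1).
- Overlap: 30 - 14 = 16 days of possible treatment after the baseline scan.
- Steroids: no washout, so the overlap can be the whole 30 days.
- Nitrosoureas and mitomycin C: washout 42 days, longer than 30, so no overlap.
- First dose should follow registration within 7 days (sections 4.1 and 4.3). Taking entry as registration, the scan can be 30 + 7 = 37 days old at first dose.

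**2. Does another section close the gap?**
- Section 5.1, within 3 days before Cycle 1: examination, performance status and laboratory tests, but no repeat disease imaging.
- Section 5 bars other agents given to treat the disease, and section 5.4.8 bars concomitant cytotoxic or investigational therapy. Both concern the treatment period, not the interval from scan to entry.
- Section 9.3 asks for response to be maintained for 8 weeks. That does not separate an earlier treatment's effect from clofarabine's.

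**3. Reproducing Rule A.** Section 13.5: continue if 8 or more of 13 respond, succeed if 14 or more of 20 respond, null 53%, alternative 80%.

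P(pass | p) = sum over x = 8 to 13 of P(X1 = x | 13, p) × P(X2 ≥ 14 - x | 7, p)

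At p = 0.53 the terms are:

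| x | P(X1 = x) | P(X2 ≥ 14 - x) | product |
|---|---|---|---|
| 8 | 0.1838 | 0.0847 | 0.0156 |
| 9 | 0.1151 | 0.2787 | 0.0321 |
| 10 | 0.0519 | 0.5654 | 0.0294 |
| 11 | 0.0160 | 0.8197 | 0.0131 |
| 12 | 0.0030 | 0.9549 | 0.0029 |
| 13 | 0.0003 | 0.9949 | 0.0003 |

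The sum from unrounded terms is 0.0932. At p = 0.80 the same formula gives 0.9085. Both match the stated 0.093 and 91%.

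**4. Sensitivity to carry-over.** Let f be the share of true non-responders scored Better because of earlier treatment. The documents give no value for f, so the range is assumed. The apparent rate is 0.53 + 0.47f.

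| f (assumed) | apparent rate | P(pass Rule A) | extra Better per 20 = 20 × 0.47f |
|---|---|---|---|
| 0 | 0.530 | 0.093 | 0 |
| 1% | 0.535 | 0.100 | 0.09 |
| 2% | 0.539 | 0.108 | 0.19 |
| 5% | 0.553 | 0.133 | 0.47 |
| 10% | 0.577 | 0.184 | 0.94 |
| 20% | 0.624 | 0.318 | 1.88 |

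This models the upward component only.

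**The case against.** - **Direction.** A reader might infer that the bias can only favour clofarabine. The documents do not support that. Growth or a new lesion between a day -30 scan and the first dose would be charged against clofarabine, because Table 3 scores new lesions as progressive. Carry-over pushes upward; the net direction is not known.
- **Frequency.** A reader might infer that carried-over regression does count. What the text supports is that it can. To be miscounted, a patient must be treated after the scan, regress despite an earlier failure, remain Better at the end of Cycle 2, and otherwise be a non-responder. The failed-regimen and active-disease criteria reduce this risk without removing it. At f of 1% or 2% the false-pass rate is 0.100 or 0.108, close to the plan's figure.
- **Not every assessment is exposed.** If the 14-day column of Table 2 governs, the skeletal survey and the examination follow the last permitted chemotherapy or radiotherapy, and the examination is repeated within 3 days of Cycle 1. The 16-day overlap then applies to the other imaging. The section 8 text gives scans 30 days, which leaves the survey window ambiguous. Steroid overlap and delayed effects remain either way.
- **Steroids on study.** A reader might infer that disease-directed steroids may continue through treatment. Section 5 bars therapies given to treat the disease other than those it goes on to describe, and the steroids described in sections 5.4.1 to 5.4.3 are for prophylaxis, capillary leak and emesis. What remains open is how that bar fits with section 3.2 item 1, and the interval between scan and entry.
- **Steroid activity.** The section 2.1 statement concerns LCH treatment in general. The text on recurrent LCH lists no steroid regimen. It shows that steroid response is possible in LCH, not how common it is after failed chemotherapy.

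These points limit the size and certainty of the concern. None of them places the baseline after the last prior treatment.

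**Conclusion.** The point holds in a limited form. The current text permits a reference scan that precedes up to 16 days of chemotherapy or radiotherapy and up to 30 days of steroid, and no other section corrects it. With no control arm and no threshold for regression, some of what is scored Better may belong to earlier treatment.

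The stated operating characteristics of Rule A are arithmetically right. The issue is what the endpoint measures. The size is unknown: the range from 0.100 to 0.318 rests wholly on the assumed f of 1% to 20%, a true rate of 53%, and no offsetting growth before the first dose. It shows how sensitive the rule is; it does not forecast the trial's error rate. The case for acting is that a short timing rule removes the overlap at little cost.

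**What to change.** **Main change.** In section 3, section 8 and Table 2, state that the baseline disease assessment used to judge response must be done after the last dose of prior disease-directed therapy, including radiotherapy, and after any start or increase of a corticosteroid given for histiocytosis, still within 30 days of entry. Add that a lesion irradiated after baseline is not used to claim regression.

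**Reconcile.** Align the 14-day and 30-day windows for the skeletal survey (Table 2 against the section 8 text). Align section 3.2 item 1, which allows steroids at entry, with the section 5 bar on other agents given to treat the disease.

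**Optional.** In section 13.6, add a supportive Rule A count in which anyone whose steroid was started or increased for histiocytosis between baseline and the End of Cycle 2 assessment is a non-responder. This needs new data collection. Section 5.2 item 7 records concomitant medication only before subsequent cycles, the section 5.1 list for Cycle 1 omits it, and Table 2 marks it only at baseline. Participants who do not start Cycle 3 would have no scheduled record at the primary assessment. The calendar would need entries before Cycle 1 and at the End of Cycle 2 assessment.

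**Cost.** Wording in three places, and an occasional early scan that must be timed later or repeated. The timing rule does not remove delayed effects of treatment completed before baseline.
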